All subjects can earn up to \$100 for completing online study assessments. The reimbursement schedule for each completed assessment is outlined in table 6 below.

Table 5. Compensation for Completion of Online Surveys

Method	Week 0	Week 4	Week 8	Week 12
Self-report Survey	\$25	\$25	\$25	\$25

Subjects randomized to the TES arm can earn additional compensation if they are interested in completing additional optional user feedback interviews. Compensation for each additional interview completed is outlined in table 6 below.

Table 6. Compensation for Completion of Optional Interviews

Method	Week 4	Week 6	Week 8
App Usability Interview	\$25	\$25	\$25
Coaching Feedback Interview	\$25		

Table 7. Compensation for Completion of Optional Focus Group

Method	Post-Trial
Focus Group (semi-structured interview guide)	\$25

Depending on Northwestern University payment guidelines and availability at the time of participation, payments to participants will be issued in one of the following ways:

- Gift card: The following gift card payment methods are available to participants earning no more than \$225 per calendar year:
 - Amazon.com gift card: Participants will be sent a code via email that will allow them to redeem an Amazon.com gift card. Gift Cards may only be redeemed toward the purchase of eligible goods and services provided by Amazon.com. Participants must create an account with Amazon to use the card. No fees apply to Amazon Gift Cards and the balance will not expire.
 - PNC Stored Value (Visa) Card: If participants do not have an Amazon account or do not wish to be compensated through Amazon, they may request a Stored Value (Visa) Card instead. The cards may be virtual or physical as per participant preference.
- Check: Participants earning more than \$225 per calendar year must be paid by check. Checks require a signed W9 form. The check may be mailed to the participant's address.

STU#:00211887

- Through Northwestern University (NU) Payroll if the participant is an NU employee

Participants will be informed that it will take approximately 2-4 weeks for payment to be processed.

WITHDRAWAL OF PARTICIPANTS

Patient participants can discontinue the TES and/or study at any time at their own request, or they may be withdrawn at the discretion of the investigator for safety, behavioral or administrative reasons.

The reason(s) for discontinuation will be documented and may include:

Patient voluntarily withdraws from treatment (follow-up permitted);

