Patient withdraws consent (termination of treatment and follow-up);

Patient is unable to comply with protocol requirements; (termination of treatment and follow-up);

Patient demonstrates disease progression (termination of treatment and follow-up unless continued treatment with study intervention is deemed appropriate at the discretion of the investigator);

RISKS TO PARTICIPANTS

Risks

During clinical trial described above, patient participants will be assessed using self-report measures over 3 months. Participants randomized to TES may be offered user feedback interviews to provide feedback on their experience using the Vira app and working with the study coach. The proposed study poses minimal risks. All potential risks associated with participation in this study will be disclosed in consent documents. Any potential risks that might exist fall into four categories: (a) risks associated with the intervention; (b) risks associated with research assessments, consisting of questions about depression, anxiety, and personal functioning, and other mental and emotional problems; (c) risks associated with potential loss of confidentiality; and (d) risks of worsening mental or emotional state. We address each in turn below.

Risks of the intervention: Digital mental health intervention programs generally have not been shown to cause any harm. The primary risk of the intervention is participants being distracted by their mobile phones while engaged in activities that demand their complete attention.

Participants occasionally try to use mobile apps while driving motor vehicles, and therefore will be instructed never to use the mobile phone while driving. Participants will be made aware of the physical, financial, and legal risks associated with using the phone while driving. If the research team becomes aware of a participant engaging in this behavior, the PI and mentors will consult to determine the most appropriate way to eliminate this risk.

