Audio data will be stored on secure servers and will only be available for coding by study staff. Interview audio files may be transcribed by one or more of the following NU transcription vendors:

GMR Transcription <https://www.gmrtranscription.com/>

Wordsworth <https://wordsworthcoop.com>

STU#:00211887

Files may be shared via secure access to FSM servers or through vendors' proprietary web-based applications for secure file management.

Data Analysis

Effectiveness (Sub-Aim 2.1).

All effectiveness analyses for the primary (PHQ-9) and secondary clinical (GAD-7, suicidal ideation) outcomes will use intention to treat methods. A comparison of population characteristics (race and ethnicity, age, gender, health status, baseline depression and use of other mental health treatments) must be made between patients receiving TES and the control treatment. Should the populations be different, propensity scores will be estimated for the likelihood of receiving TES, and models will adjust for those scores (trimming the data as necessary). After the population comparison and appropriate adjustment, we will compare overall effectiveness, using generalized linear mixed models (GLMM) to determine if there are differences in effectiveness between individuals receiving TES and CT over time.¹⁰⁶ Separate models will be run for PHQ-9 and GAD-7, using participants who meet entry criteria for each (PHQ-9 \geq 10 or GAD-7 \geq 8, respectively). Missing data will be managed through multiple imputation. Additional covariates will also be included to identify any substantive changes in the service, technologies, and/or implementation plan as a result of optimization during the trial.

Moderation of TES on effectiveness. Moderation of patient characteristics (race, ethnicity, income, age, sex, health status, substance/alcohol use, or use of other mental health treatments, including pharmacologic) will be analyzed in individual GLM models by estimating a treatment by moderator interaction in predicting end of treatment depression scores adjusting for baseline levels of depression.

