### **Statistical Analysis Plan**

All effectiveness analyses for the primary (PHQ-9) and secondary clinical (GAD-7, suicidal ideation) outcomes will use intention to treat methods. A comparison of population characteristics (race and ethnicity, age, gender, health status, baseline depression and use of other mental health treatments) must be made between patients receiving TES and the control treatment. Should the populations be different, propensity scores will be estimated for the likelihood of receiving TES, and models will adjust for those scores (trimming the data as necessary). After the population comparison and appropriate adjustment, we will compare overall effectiveness, using generalized linear mixed models (GLMM) to determine if there are differences in effectiveness between individuals receiving TES and CT over time. Separate models will be run for PHQ-9 and GAD-7, using participants who meet entry criteria for each (PHQ-9 > or = 10 or GAD-7 > or = 8, respectively). Missing data will be managed through multiple imputation. Additional covariates will also be included to identify any substantive changes in the service, technologies, and/or implementation plan as a result of optimization during the trial. Moderation of TES on effectiveness. Moderation of patient characteristics (race, ethnicity, income, age, sex, health status, substance/alcohol use, or use of other mental health treatments, including pharmacologic) will be analyzed in individual GLM models by estimating a treatment by moderator interaction in predicting end of treatment depression scores adjusting for baseline levels of depression.

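### The withdrawal rules let outcome follow-up end for non-compliance or disease progression, which undercuts the intention-to-treat analysis and can bias it modestly, in an uncertain direction

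*Protocol*

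**What the plan says.** Protocol, Withdrawal of Participants, lists reasons for discontinuation and gives each its own consequence for follow-up:

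- Leaving treatment by choice: "Patient voluntarily withdraws from treatment (follow-up permitted").
- Non-compliance: "Patient is unable to comply with protocol requirements; (termination of treatment and follow-up"), with no exception.
- Progression: "Patient demonstrates disease progression (termination of treatment and follow-up", with an exception in the same parenthesis where the investigator, using discretion, judges continued study treatment appropriate). Follow-up is therefore kept only if study treatment is kept.

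The same section makes removal discretionary: besides leaving at their own request, "they may be withdrawn at the discretion of the investigator for safety, behavioral or administrative reasons".

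On analysis, the SAP states: "All effectiveness analyses for the primary (PHQ-9) and secondary clinical (GAD-7, suicidal ideation) outcomes will use intention to treat methods". The protocol's Data Analysis section, Effectiveness (Sub-Aim 2.1), says the same. On gaps in the data, the SAP says only "Missing data will be managed through multiple imputation". Neither document names the imputation variables, a missingness assumption or a sensitivity analysis.

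Elsewhere the protocol expects patients to stop treatment and stay in the study. RCT Procedures Involved and Failure to Initiate Treatment give such patients a one-question survey about their reason.

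**The concern.** An intention-to-treat comparison needs outcomes on randomised patients whatever their adherence or clinical course. Two of the listed reasons let outcome collection stop because of adherence or course. In a trial whose primary outcomes are PHQ-9 and GAD-7 severity, undefined progression most naturally means worsening on those scales, so a missing score may be missing because it would have been high. The surveys are self-report, completed online or by phone, so the end of treatment is no practical reason to end them.

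At stake is whether the week 8 and week 12 comparison rests on observed outcomes or, for some of the worst-faring patients, on an imputation model that the plan does not describe.

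**Working it through.** **Passages side by side.** The plan separates end of treatment from end of follow-up for voluntary leavers but not for the other two reasons. A patient who stops using the app is kept and surveyed under Failure to Initiate Treatment, yet could be classed as non-compliant and lost under Withdrawal of Participants. The documents do not say which applies.

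**Inputs from the plan.** The only relevant figures are in the protocol's Power paragraph under Data Analysis: SD 5, effect size 0.62, and 50 CT and 80 TES patients. 0.62 × 5 = 3.1 points reproduces the stated difference. The plan gives no expected number of withdrawals, so all sizes below rest on assumptions.

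**Assumed model.** Scores at baseline, week 4 and week 8 (Y0, Y4, Y8) are normal with SD 5 and baseline mean 15. Mean improvement in CT by week 8 is m, and TES improves by a further δ; half of each change is present at week 4. Follow-up ends with probability p if the score rises from baseline by at least a threshold. Missing Y8 is imputed within arm from Y0 and Y4, and the estimate is the difference in week 8 means.

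**Case 1: the trigger is recorded at week 4 and used in the imputation.** With δ = 3.1, m = 3, equal correlations of 0.4 to 0.6, thresholds of 1, 3 or 5 points and p = 1 in both arms, 7–32% of CT and 4–23% of TES patients lose week 8. Imputation returns about 3.1, so there is no bias. Loss in TES only, with the trigger recorded at week 4, also gives a bias of about 0.

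**Case 2: the trigger is a worsening that no outcome visit records.**

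| Scenario | Assumptions | Result |
|---|---|---|
| No true effect; half of TES worseners lost, no CT loss | correlations 0.6 (baseline with later visits) and 0.75 (week 4 with week 8), m = 3; any rise, 2+ or 5+ points | spurious TES benefit 0.41, 0.27, 0.09 |
| Same | any rise; m = 1, 3, 5, 7 | 0.57, 0.44, 0.29, 0.15 |
| True effect 3.1; half of worseners lost in each arm | as row 1 | estimate 2.85 to 3.01 |
| True effect 3.1; all worseners lost in each arm | equal correlations 0.4 to 0.6, m = 3; thresholds 1, 3, 5 | estimate 2.2 to 2.9 |

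Rows 1 and 2 come from separate runs, which agree to a few hundredths where they overlap. A high threshold combined with a large mean improvement would give less than either row shows. In row 4, 4–23% of CT and 1–10% of TES patients are lost. The dilution is 3.1 − 3.01 = 0.09 to 3.1 − 2.85 = 0.25 points in row 3, and 3.1 − 2.9 = 0.2 to 3.1 − 2.2 = 0.9 in row 4.

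**Scale.** The unadjusted standard error of the arm difference with the plan's numbers is 5 × √(1/50 + 1/80) = 0.90 points. The first two rows span about 0.09/0.90 = 0.1 to 0.57/0.90 = 0.6 of a standard error. No SD is given for GAD-7, so no size is given for it.

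**The case against.** Several points on the other side stand.

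- Nothing here is automatic. The investigator may withdraw a patient, the list gives reasons that may apply, and progression has an exception. A reader might infer that every patient who worsens is removed; the text does not say so. The exception does not cure the problem, because it covers progression only and still ties follow-up to staying on treatment.
- The suicidality procedures under Protections Against Risk do not list ending treatment or follow-up as a response.
- A reader might infer that the rule flatly contradicts intention to treat, or that imputation cannot work. Neither follows. All randomised patients can be analysed as randomised with imputed values, and Case 1 shows that imputation succeeds when the trigger is recorded and used. The plan does not secure that condition.
- A reader might infer that worsening is noticed only in TES, so that the bias must favour TES. Only TES has a coach and feedback interviews, but the PHQ-9 surveys and the weekly suicidality monitoring are not limited to TES. Losing half of TES worseners and no CT worseners is therefore an extreme assumption.
- Non-compliance is also undefined. If it means not answering surveys, the scores would be missing under any rule.
- The trial is described as a feasibility pilot whose size was not set by power, and reasons for discontinuation are already to be documented.
- The Protected Health Information section says that about 114 participants have completed the study, so new wording cannot recover their data.

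**Conclusion.** The point holds as an inconsistency with a modest potential for bias. Where the two withdrawal reasons are applied, primary outcome data are lost for reasons linked to outcome or adherence. That weakens the promised intention-to-treat analysis and sits poorly with the sections that keep patients in the study after they stop treatment.

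The direction is uncertain: towards TES if worsening is noticed more often through the coach and interviews, towards no difference if detection is equal. About 0.1 to 0.6 PHQ-9 points is an illustration for half of TES worseners and no CT worseners lost. It depends on the assumed threshold, mean improvement and correlations, and on the worsening going unrecorded. If nobody had follow-up ended for these reasons, there is no bias from this source. No view is taken on when treatment should stop.

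**What to change.** **Protocol.** Reconcile Withdrawal of Participants with RCT Procedures Involved, Failure to Initiate Treatment and the Data Analysis section. Suggested sentence: *Ending study treatment because of progression or inability to comply does not end outcome assessment; the week 4, 8 and 12 surveys continue unless the participant withdraws consent for follow-up.* Leave the treatment-discontinuation rules as they are.

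**SAP, which also serves participants who have already finished.**

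1. Report by arm how many participants had follow-up ended for progression and how many for non-compliance, with the last visit observed. If there were none, say so.
2. Name the imputation model, and include arm and every recorded PHQ-9 and GAD-7 score.
3. Add a delta-adjusted missing-not-at-random analysis for these participants: worsen their imputed scores by a range of amounts, separately by arm. An arm mean shifts by the proportion affected times delta. For example, 10% affected and a delta of 5 points (one assumed SD) move it by 0.10 × 5 = 0.5 points.

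**Cost.** One protocol sentence, a short SAP addition, and at most 3 × $25 = $75 in survey payments per affected participant.

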RCT Timeline of Participant Activities

Active participation will last 12 weeks for each study participant. Participants will use the study apps and receive coaching (group 1 only) for the first 8 weeks. We will unobtrusively track all communication with the study coach. Assessment will continue through week 12. Study assessment milestones are laid out in tables 3 and 4 below.

Table 2. Online surveys to be administered to all participants

Method	Week 0	Week 4 Mid-Treatment	Week 8 End of Treatment	Week 12 Post-Treatment
Self-report Survey	x	x	x	x
App Usage	Continuous, unobtrusive			

Table 3. Optional interview data to be collected from patients randomized to TES

Method	Week 4 Mid-Treatment	Week 6	Week 8 End of Treatment
Vira app usability interview	x	x	x
Coaching user-feedback interview	x		

Table 4. Optional focus group be completed with patients randomized to control and TES

Method	Post-Trial Completion
Focus Group (semi-structured interview guide)	x

The anticipated completion date for primary analyses is March 31st, 2024.

RCT INCLUSION AND EXCLUSION CRITERIA:

Trial participation will be offered to patients at Rush University Medical Center aged 13 or older. Children under the age of 13 will be excluded given likely differences in development and

STU#:00211887

smartphone ownership that would make such young children an inappropriate population for evaluating the technology enabled service and implementation plan.

Inclusion Criteria: US Citizen/Resident (for payment purposes) living in the US during the 12-week study period (for tech functionality, data security, and safety management purposes), 13 years or older (if age 13-17, parent/caregiver must provide consent, a consent process is in place for English-speaking minors with Spanish-speaking parents), English speaking, eligible to receive care through Rush University Medical Center or its clinical affiliates, owns an Android or iPhone smartphone with an up-to-date operating system, has used a smartphone in the last 7 days, at least moderate symptoms of depression (PHQ-9 greater than or equal to 10) and/or anxiety (GAD-7 greater than or equal to 8)

Exclusion Criteria: Severe suicidality (as defined by presence of a plan + intent to act on that plan)

VULNERABLE POPULATIONS

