of engagement relative to the CT, with by testing the mediational effects of subjective and objective engagement with the apps on the primary outcomes, depression (PHQ-9) and anxiety (GAD-7). Subjective engagement will be measured using the Twente Engagement with eHealth Technologies Scale (TWEETS), while objective engagement will be measured by app use (number of app launches and time from first to last use). We hypothesize that the difference between the TES and CT will be mediated by subjective and objective engagement. We also hypothesize the moderating effects of patient characteristics on subjective and objective engagement, depression, and anxiety will be lower in the TES arm, relative to CT, as a result of inclusion of users' voices through the design processes used in the creation of the TES app.

Mediation will be tested using methods by Iacobucci.¹²¹ Using analogous adaptations of methods to Preacher's methods,^{122,123} we will be able to test for moderation and mediation together. Between patient characteristics and actionable targets (subjective and objective use) we could test many moderated mediation (conditional indirect effects) which may indicate that a particular subset of participants (defined by subjective or objective use, and patient characteristics) may be more likely to benefit from TES. Multiple models will need to be fit, increasing the possibility of an inflated type I error. To prevent this, we will implement a false discover rate (FDR) control using methods by Benjamini-Hochberg¹²⁴ although as these are pilot studies, we will test these models at a FDR of 10%. Depending on the distribution of the variables under consideration, we will fit linear or logistic regression models to estimate regression parameters a (TES and the relationship to potential mediators) and b (mediator relationship to the outcome). Iacobucci shows that a normally distributed test statistic can be constructed from standardized regression parameters $Z_a = a/SE_a$ such that $Z(\text{mediation}) = Z_a * Z_b / (\sqrt{Z_a^2 + Z_b^2 + 1})$ can be used to test for mediation. Further, we can examine if there is further moderation of these models such that any patient covariate could moderate the relationship between TES use and depression outcomes. Power analyses for the individual RPs can be found in the RPs.

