Power. While sample size and power calculations for mediational analyses are subject to speculation, Fritz and MacKinnon¹¹⁶ show that our effective sample size of 112 (130 divided by the design effect determined by the number of patients per clinic and ICC within clinic) achieves 80% power to detect between a medium effect size, and small-medium effect size for the a and b paths (medium ES = 0.39, small-medium ES=0.26) using the joint tests we propose.

SMS Data and Focus Group Analysis Plan

Data from SMS records and focus groups will be analyzed qualitatively via thematic analysis as described by Braun and Clarke or via semi-open iterative coding. Semi-open iterative coding would allow us to begin with a set of codes relevant for the trial and stay open to new codes (as in thematic analysis).

Organizational Level Data

Rush University Medical Center personnel will provide aggregated data on TES Reach/Adoption on a routine basis. The Rush team will ensure a de-identified DUA is in place and will work with the Research Core to have the data extracted and de-identified prior to the transfer. Additionally, the request will be reviewed and approved by the Rush Data Governance Committee. These de identified data exports may include the following information which will enable the study team to understand what proportion of patients who screened positive for depression and/or anxiety were offered participation in the trial and engaged in TES. For patients in each participating clinic:

- Number of patients screening positive on PHQ-9, GAD
- Number of patients being referred to study

PROVISIONS TO MONITOR THE DATA TO ENSURE THE SAFETY OF PARTICIPANTS

STU#:00211887

CLINICAL TRIAL

Oversight of the trial is provided by the Principal Investigators, Drs. [name], [name], and [name]. The NU research coordinator, [name] will ensure that informed consent is obtained prior to engaging in research activities, and that the study is conducted according to the IRB-approved research plan.

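### The Aim 3 mediation models name no baseline outcome score, so the non-randomised engagement-to-outcome path is open to confounding by baseline severity

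*Protocol*

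**What the plan says.** Under Data Analysis, D6.3 Aim 3 (Experimental Therapeutics), the protocol hypothesises that subjective and objective engagement mediate the TES-CT difference. It will fit linear or logistic regressions for "regression parameters a (TES and the relationship to potential mediators) and b (mediator relationship to the outcome" and combine the two into Z(mediation). No covariate, outcome time point or analysis population is given. The many resulting models are controlled by Benjamini-Hochberg at a false discovery rate of 10%. The SAP has no mediation text.

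Other parts of the plan bear on this:
- **RCT Inclusion and Exclusion Criteria:** a patient qualifies with "at least moderate symptoms of depression (PHQ-9 greater than or equal to 10) and/or anxiety (GAD-7 greater than or equal to 8"), so one symptom is enough.
- **Effectiveness (Sub-Aim 2.1) and SAP:** "Separate models will be run for PHQ-9 and GAD-7, using participants who meet entry criteria for each".
- **Moderation of TES on effectiveness:** the models predict "end of treatment depression scores adjusting for baseline levels of depression".
- **Power paragraph after Aim 3:** it rests on "our effective sample size of 112 (130 divided by the design effect determined by the number of patients per clinic and ICC within clinic").
- **RCT Procedures Involved:** PHQ-9 and GAD-7 are measured at baseline and at weeks 4, 8 and 12, so a baseline score exists for each outcome.

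**The concern.** Randomisation protects path a (arm to engagement). It does not protect path b (engagement to outcome), because patients choose how much they use the app. Baseline severity predicts the final score and may also predict app use. If less depressed patients open the app more, b is negative even when engagement does nothing, and Z(mediation) reads this as benefit passing through engagement. False discovery rate control does not help: it deals with the number of tests, not with a biased test statistic.

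The either-symptom entry rule makes this worse. A patient who enters on anxiety alone starts with PHQ-9 below 10 and will tend to finish low, so the baseline range is wider than in a depression-only sample. The same holds for GAD-7 with depression-only entrants. At stake is the central Aim 3 claim about why the TES works.

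**Working it through.** **The plan's own figure.** 130/112 = 1.161. With the protocol's ICC of 0.01, the implied clinic size is 1 + 0.161/0.01, about 17 patients. The number of clinics is not given. Seven, eight or nine equal clinics give 130/[1 + (m - 1) x 0.01] = 110.6, 112.8 and 114.6. So 112 is plausible but cannot be confirmed.

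**Inputs from the protocol.** N = 130 split 50 CT / 80 TES (Power paragraph under Effectiveness); the entry rule; Z = ZaZb/sqrt(Za^2 + Zb^2 + 1).

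**Inputs assumed, because the documents give none.**
- Anxiety-only share about 25%.
- Baseline PHQ-9 about N(15, 3.5) in patients at or above 10, and N(6, 2) in anxiety-only entrants.
- Follow-up = 4 + 0.5 x baseline + noise of SD 4.
- Direct arm effect -1.5 points (30% of that in anxiety-only entrants).
- No effect of engagement on outcome.
- Arm effect on engagement 0.5 to 0.8 SD; engagement-baseline correlation 0 to -0.3.
- Arm kept in the b model.

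**Hand check.**
1. Expected Za = d/sqrt(1/50 + 1/80) = d/0.180, which is 2.77 for d = 0.5 and 4.44 for d = 0.8.
2. |Z| > 1.96 needs Zb^2 > 3.84(Za^2 + 1)/(Za^2 - 3.84), so |Zb| > 2.94 or 2.24. The test is therefore conservative when b is unbiased.
3. Baseline variance, ignoring truncation: 0.25 x 0.75 x 9^2 + 0.75 x 3.5^2 + 0.25 x 2^2 = 25.4, so SD 5.04.
4. Spurious b at correlation -0.3: 0.5 x 5.04 x 0.3 = 0.76 points per SD of engagement. Residual SD = sqrt(16 + 0.25 x 25.4 x 0.91) = 4.67, standard error 4.67/sqrt(130) = 0.41, expected |Zb| = 1.85. At -0.2 the same steps give 1.22.
5. Chance of crossing the limits in step 2: about 14% and 35% at -0.3, and 4% and 15% at -0.2.

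**Simulation.** This lets Za vary. Single test, two-sided 5%, before FDR control. Each range runs from arm effect 0.5 SD to 0.8 SD.

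| Correlation | False mediation, no baseline |
|---|---|
| 0 | 1-3% |
| -0.1 | 2-4% |
| -0.2 | 5-13% |
| -0.3 | 12-28% |

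With baseline PHQ-9 in both models, all 130 patients, the rate is at most about 3% throughout.

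**Is mixed entry the cause?** With no anxiety-only entrants the baseline SD is 3.5. Step 4 at -0.3 then gives 0.5 x 3.5 x 0.3 = 0.53, residual SD sqrt(16 + 0.25 x 12.25 x 0.91) = 4.33, and |Zb| = 1.38 instead of 1.85. The simulated false rate still reaches about 16% at 0.8 SD. Mixed entry amplifies the error; the missing baseline term produces it.

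**Second data model.** Patients are screened on correlated scores: PHQ-9 mean 11, GAD-7 mean 9, both SD 5, correlation 0.6. The follow-up slope on baseline is 0.6 and there is no TES effect on outcome; about 81% of entrants meet each cut-off. At correlation size 0.3, the false rate in all 130 without baseline is 13.2% (0.5 SD) to 31.1% (0.8 SD). In PHQ-9 >= 10 patients without baseline it is 3.4% to 10.2%. With baseline it is at most 3.1% in either population. Restriction alone reduces the error but does not remove it.

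**Power.** With a true engagement effect (-1.5 points per SD, 30% of that in anxiety-only entrants; correlation 0; 1:1 allocation) and 20% / 30% anxiety-only:
- all patients, no baseline: 0.78 / 0.68
- all patients, with baseline: 0.88 / 0.82
- PHQ-9 >= 10 only, with baseline: 0.86 / 0.77

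**The case against.** The best defence is that the text is silent rather than wrong. It does not mention arm in the b model either, and it cites published mediation methods, so baseline may be intended. That is fair: the documents do not say that baseline is left out. But an analyst who follows the text literally fits the vulnerable model, and the moderation paragraph shows that the authors state baseline adjustment where they plan it.

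A reader might infer from the 130 in the Aim 3 power paragraph that all randomised patients enter the mediation models, in a different population from the effectiveness analysis. The documents do not support that as fact. The effectiveness power paragraph also starts from 50 + 80 = 130, although that analysis is restricted by "using participants who meet entry criteria for each". Enrolled numbers are used for power even where the analysis set is smaller, so the mediation population is simply unstated.

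It is also fair that the larger percentages need a correlation of at least 0.2 in size, which no document reports, and that this is a pilot with openly relaxed error control. Both points limit the weight of the concern. Neither is a reason to leave out a covariate that is already collected.

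**Conclusion.** The concern holds as a gap in model specification that should be closed. Without a baseline score, Z(mediation) is exposed to confounding of path b whenever baseline severity and engagement are related. Under the assumptions above, the single-test false rate is near or below nominal at correlations of 0 to -0.1, and rises to 5-13% at -0.2 and 12-28% at -0.3. With baseline it is at most about 3%. These figures are conditional on the assumed inputs and come before FDR control; they are not the plan's error rate.

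It would be tempting to say that low-scoring entrants create the false result and that restricting each model to its own symptom set is the cure. The working does not bear that out: the error persists without such entrants, and baseline adjustment controls it with them. The effectiveness analyses of PHQ-9 and GAD-7 are not affected.

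**What to change.** In the Aim 3 analysis text, and in a mediation section added to the SAP:

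1. Include the baseline score of the outcome analysed (PHQ-9 or GAD-7) as a covariate in both the mediator (a) model and the outcome (b) model.
2. State that treatment arm stays in the b model.
3. State the population for each mediation model. Baseline-adjusted models in all randomised patients control the false rate and keep power. Models in the symptom-specific effectiveness sets can be reported alongside, so that the mediated effect can be set against the total effect in the same patients.
4. If the symptom-specific sets are made primary, restate the 130 and 112 in the Aim 3 power paragraph. If 60% to 90% of patients qualify, the effective number is 112 x 0.6 = 67 to 112 x 0.9 = 101. Joint-test power for paths of 0.39 and 0.26 is then about 0.47 to 0.69, against 0.75 at 112.

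The cost is wording only; no new data are needed. Baseline adjustment does not remove confounding by unmeasured drivers of engagement, so the mediation result should still be reported as exploratory.
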